8. ANALYSIS SETS

The following analysis sets for the Induction Treatment Period are defined as follows:

Full Analysis Set (FAS): The FAS consists of all randomized participants receiving at least 1 dose of study treatment. Under this approach, participants are counted in the treatment group to which they were randomized, regardless of the treatment received during the study.

Modified Full Analysis Set (mFAS): For a given endpoint (see [Section 23](#), Appendix II), mFAS consists of all randomized participants who received at least 1 dose of study treatment and contribute at least one complete endpoint assessment for at least one post-baseline Induction visit. Participants will be analyzed according to the treatment to which they were randomized.

Per Protocol (PP) Set: The PP Set consists of all participants in the primary endpoint mFAS who received $\geq 80\%$ and $\leq 120\%$ of study treatment and do not have a protocol deviation preventing contribution to the primary analysis of the primary efficacy endpoint. Participants experiencing an intercurrent event during the Induction Treatment Period and not experiencing other deviations preventing contribution to the primary and key secondary analyses of the primary and key secondary efficacy endpoints will be included in the PP set and treated as non-responders in these analyses ([Section 3.5](#)).

Safety Set: The Safety Set consists of all randomized participants who received at least 1 dose of study treatment. For this population, participants are analyzed according to the treatment received, regardless of randomization. The Safety Set will be used for all safety analyses in the Induction Treatment Period.

The following analysis sets for the LTE and OLE Treatment Periods are subsets of the analysis sets of the Induction Treatment Period, as defined below:

FAS-Extension Treatment (FAS-ET) Set: The FAS-ET Set consists of all randomized participants who received at least 1 dose of study treatment in the LTE or the OLE Treatment Period. Under this approach, the original treatment groups as assigned at randomization will be used throughout LTE. In general, participants will be analyzed according to protocol-specified intended study treatment dose in FAS-ET analyses. Additional details are provided for specific analyses described elsewhere in this SAP.

Safety-Extension Treatment (Safety-ET) Set: The Safety-ET Set includes all participants who received at least 1 dose of study treatment in the LTE or the OLE Treatment Periods. The Safety-ET Set will be used for all safety analyses. In general, participants will be analyzed according to actual study treatment dose in Safety-ET analyses. Additional details are provided for specific analyses described elsewhere in this SAP.

9. GENERAL CONSIDERATIONS

9.1 Summary Statistics

In general, continuous variables will be summarized using the following standard descriptive summary statistics: number of observations, mean, standard deviation (SD), minimum, first quartile, median, third quartile, maximum, and number of missing observations. Use of decimal places in descriptive statistics will be as follows:

- Min, Max: same as the actual data (but not more than 4 decimals)

- Mean, Geometric Mean, Median, First Quartile, Third Quartile: actual data + 1 decimal (but not more than 4 decimals)
- SD, Geometric SD: actual data + 2 decimals (but not more than 4 decimals)
- Geometric CV: 2 decimals (but not more than 4 decimals)

Categorical data will be described using frequency counts and percentage. Percentages will be based on the number of participants in the selected analysis set and relevant treatment group unless otherwise stated. Percentages will be rounded to one decimal place except for one hundred percent, which will be presented as 100%. Tests will use a two-sided alpha=0.05 unless otherwise specified.

9.2 OLE Visit Labels

Visit labels for the OLE in the EDC system are different between Protocol version 1.0 and later protocol versions. Refer to [Section 24](#) (i.e., Appendix III) for a visit matrix mapping that allows a common OLE visit label schema across all participants regardless of the protocol version.

9.3 Reference Start Date and Study Day

Study Day will be calculated from the reference start date and will be used to show start/stop day of assessments and events. Reference start date is defined as the date of the first dose (i.e., Day 1) and will appear in every listing where an assessment date or event date appears.

- If the date of the event is on or after the reference start date, then:

$$\text{Study Day} = (\text{date of event} - \text{reference start date}) + 1$$

- If the date of the event is prior to the reference start date, then:

$$\text{Study Day} = (\text{date of event} - \text{reference start date})$$

In the situation where the event date is partial or missing, Study Day and any corresponding durations will appear missing in the listings.

9.4 Body Mass Index

Body mass index is calculated from Screening weight (kg) and height (m) and retains one significant digit to the right of the decimal prior to summarization:

$$\text{BMI (kg/m}^2\text{)} = [\text{weight in kilograms}] / [(\text{height in meters})^2]$$

9.5 Baseline

The last non-missing assessment made prior to the first dose of Induction Treatment Period study treatment (including unscheduled assessments) will be used as baseline for both the Induction Treatment Period and LTE. In the event a participant is randomized but never treated, the randomization date will be used instead of the date of first dose of study product. OLE may utilize two different baselines:

- Last non-missing assessment made prior to the first dose of Induction Treatment Period study treatment (including unscheduled assessments)
- Last non-missing assessment prior to the first dose of OLE study treatment (including unscheduled assessments)

If measurements include time, the date/time will be used to define Baseline. Otherwise, only dates will be compared. In the event the last non-missing observation and date of first dose have the same date and time of day is not collected, if the measurement was planned per protocol to be captured prior to the first dose, the measurement will be considered Baseline.

9.6 Windowing Conventions

All scheduled study visits are defined relative to Study Day 1, the date of first Induction Treatment Period dose.

Scheduled visit windows for the Induction Treatment Period are defined in Protocol VTX002-201 Section 1.2 Table 1. Scheduled visit windows for the LTE are defined in Protocol VTX002-201 Section 1.2 Table 2. Scheduled visit windows for the OLE are defined in the Protocol VT002-201 Section 1.2 Tables 3, 4, 5, and 6.

A windowing convention will be used to determine the analysis visit value for a given measurement and will be applicable for all by-visit summaries and analyses for efficacy and safety data. Refer to [Table 3](#) for specific Induction Treatment Period visit windows.

Windowing will be applied prior to any missing data calculations. The last non-missing measurement taken prior to Day 1 (including unscheduled assessments) will be labeled as Baseline. Unless stated otherwise, data from scheduled, unscheduled, and early termination site visits will be eligible for allocation to an analysis visit. Follow-up visit data is handled as-is.

Table 3. Analysis Visit Windows

	Visit Label	Study Week	Ideal Study Day (Study Day)	Protocol Visit Window (Study Day)	Analysis Visit Window (Study Day)
Non-Efficacy, Physician's Global Assessment (PGA), IBDQ ^a	Visit 1/Baseline	n/a	-14	[-28, -1]	≤1
	Visit 2	0	1	[1]	[1, 4]
	Visit 3	1	8	[8, 10]	[5, 18]
	Visit 4	4	29	[26, 32]	[19, 42]
	Visit 5	8	57	[54, 60]	[43, 63]
	Visit 6	10	71	[68, 74]	[64, 81]
	Visit 7	13	92	[89, 95]	[82, 102]
Endoscopy and Colonic Biopsy ^b	Visit 1/Baseline	n/a	-14	[-28, -1]	≤1
	Visit 7	13	92	[89, 95]	[76, 108]
SF and RB calculated from eDiary entries ^{b, c}	see footnote	see footnote	see footnote	see footnote	see footnote
Early Term /Unscheduled ^d	see footnote	see footnote	see footnote	see footnote	see footnote
1-Week Follow-up ^d	1-Week Follow-up	n/a	X+7	n/a	n/a
2-Week Follow-up ^d	2-Week Follow-up	n/a	X+14	n/a	n/a

^a Analysis visit windows and Ideal Study Days are intended to map, to Study Visits, all by-visit data collected during the Induction Treatment Period.

^b When endoscopy occurs: SF and RB scores are computed using a 7-day look back window whose ending Study Day is immediately prior to the first day of bowel preparation, and these SF and RB scores are attached to the endoscopy. If no bowel preparation is performed for a given endoscopy, the 7-day look back window ends at the Study Day immediately prior to the endoscopy. If the endoscopy occurs outside of both Visit 1/Baseline and Visit 7 analysis windows for endoscopy, the SF, RB, ES, and histopathology data for the endoscopy are not associated with any analysis visit and are listed only. If the endoscopy occurs inside either the Visit 1/Baseline or Visit 7 endoscopy analysis window, the SF, RB, ES, and histopathology data are associated with Visit 1/Baseline or Visit 7 as appropriate. If multiple endoscopies are associated with the same Visit 1 or Visit 7 analysis visit window, the following sequential steps will be applied to choose a unique endoscopy to associate with the analysis visit: [i] endoscopies with missing ES scores are dropped from consideration and, [ii] if there are remaining endoscopies to choose from, the most recent endoscopy is kept. After determining a unique endoscopy to associate with the analysis visit, if the 7-day look back window overlaps with a previous set of endoscopy and/or bowel preparation dates, the eDiary SF and RB values for those overlapping dates will be set to missing for computational purposes.

^c For a given post-baseline analysis visit, if no endoscopy is associated with that analysis visit SF and RB will be computed using a 7-day look back window whose ending Study Day is immediately prior to the site visit closest to the Ideal Study Day when a within-window site visit exists. If two site visits are equidistant from the Ideal Study Day, the earlier site visit is chosen. If no site visit is associated with the given post-baseline analysis visit, SF and RB will be not be computed for that visit. If the 7-day look back window overlaps with a previous set of endoscopy and/or bowel preparation dates, the eDiary SF and RB values for those overlapping dates will be set to missing for computational purposes.

^d Post-baseline ET and Unscheduled visits may include endoscopy and analysis visit windows are applied to ET and Unscheduled visit data in a manner identical to that of other visits. Endoscopy data from ET and Unscheduled visits may not be associated with any analysis visit other than Visit 7. Endoscopy

data from ET and Unscheduled visits not associated with Visit 7 will be listed only. 1-Week and 2-Week Follow-up data is not windowed and presented according to nominal visit label in tables.

For composite scores such as MMS, if one or more components is missing from an analysis visit window the composite score is missing. If one or more results for a variable are assigned to the same analysis visit, the result with the date closest to the protocol Ideal Study Day will be used in the analysis, except for rectal bleeding and stool frequency component subscores used in the determination of Symptomatic Remission, Symptomatic Response, MMS, or total MCS. In this case, 7-day look-back windows anchored to either an endoscopy or a site visit are used to determine the component subscores.

If two measurements in the same analysis visit window are equidistant from the protocol scheduled study day, the earliest measurement will be used in the analysis. If multiple assessments are available on the same day, then the average of the assessment will be used in the analysis, except for laboratory data where the assessment at the earliest time of the same day will be used. Central laboratory assessments will be used in both summaries and listings, while local laboratory assessments will only be separately listed. Local laboratory data may be used by investigators to help inform participant safety decisions and adverse event reporting.

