6.5 Guidance for Cardiac Monitoring Following Treatment Initiation or Reinitiation

Prerandomization (ie, predose on Day 1) ECG should be performed and assessed prior to randomization.

Following treatment initiation or reinitiation, participants will remain in the clinic for at least 6 hours after study drug administration for safety assessments.

Prerandomization (ie, predose on Day 1) vital signs (ie, pulse, systolic and diastolic BP, temperature, and respiratory rate) will be used as baseline measurements. Pulse and BP will be measured using calibrated equipment (as appropriate) after the participant has been sitting for at least 5 minutes.

Atropine and epinephrine should be readily available at all study sites. Availability of emergency equipment should be within close proximity to study site. Personnel experienced in the use of advanced life support must be readily accessible during the first-dose monitoring (Week 0 [Day 1/Visit 2] and OLE Week 0 [OLE Day 1/OLE Visit 1]) and reinitiation of treatment, as well as in case of an emergency. A member of the Investigator team should be available to monitor the participant for the 6-hour monitoring period and report any abnormalities to the Investigator.

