12. DEMOGRAPHIC AND BASELINE CHARACTERISTICS

The following demographic variables will be summarized, as collected in EDC:

- Baseline Age (yr)
- Baseline Age Group (18-<65 ≥65)
- Baseline Height (cm)
- Baseline Weight (kg)
- BMI (kg/m²), derived from Screening weight (kg) and height (m)
- Baseline eGFR (mL/min/1.73m²), derived from serum creatinine using the 2021 update to the CKD-EPI formula
- Country
- Sex (M/F)
- Female of Childbearing potential (Y/N)
If No:
 - Surgical Sterilization or Hysterectomy (Y/N)
 - Post-menopausal for more than 1 year (Y/N)
- Ethnicity
- Race

Separately, Baseline¹ UC signs and symptoms will be presented, where Baseline is understood to be the most recently available measurement prior to administration of study treatment. For these UC Baseline signs and symptoms, stool frequency and rectal bleeding data derived from eDiary will be presented, as opposed to what is available from EDC. Refer to [Section 10.3](#) for a description of how eDiary data is processed to determine the stool frequency and rectal bleeding subscores. Derived stool frequency and rectal bleeding data will also be used for efficacy endpoint evaluation, and if these values are present in EDC but not calculable from eDiary, they will be treated as missing. The following UC Baseline signs and symptoms will be summarized descriptively:

- Duration of Ulcerative Colitis (yr): (Informed consent date – Date of diagnosis + 1) / 365.25
- Location and extent of Ulcerative Colitis (Proctosigmoiditis, Pancolitis, Proctitis, Other)
- Any surgeries related to Ulcerative Colitis? (Y/N)
If Yes:
 - Number of surgeries
- Colonoscopy within past 12 months? (Y/N)
- Endoscopic Score (ES)
- Stool Frequency (SF)
- Rectal Bleeding (RB)
- Physician’s Global Assessment (PGA)
- Mayo Clinic Score (MCS)
- Modified Mayo Score (MMS)
 - MMS Group (5-6, 7-9)
 - As collected in IWRS
 - As collected in EDC
- Partial Mayo Score (PMS)
- Stable corticosteroids (Y/N)
 - As collected in IWRS
 - As collected in EDC

¹ Baseline refers to the most recently available measurement(s) prior to administration of study treatment. For some UC signs and symptoms, such as Endoscopic Score, this is strictly a Screening data point. For others such as Physician’s Global Assessment (PGA) and MCS (which uses PGA as a component), these are Study Day 1 pre-dosing values.

- Prior biologic/JAK (Y/N)
 - As collected in IWRS
 - As collected in EDC
 - Prior failure of anti-TNF (Y/N) as collected in EDC

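### The SAP 9.6 rule that Baseline is the last value before Day 1 contradicts SAP 9.5 and the SAP's own Table 3, and taken literally removes or replaces Day 1 predose baselines

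*SAP*

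**What the plan says.** SAP 9.5, the section devoted to baseline, reads: "The last non-missing assessment made prior to the first dose of Induction Treatment Period study treatment (including unscheduled assessments) will be used as baseline". Where a measurement carries a time, date and time decide. Where it shares the date of first dose and has no time, "if the measurement was planned per protocol to be captured prior to the first dose, the measurement will be considered Baseline".

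SAP 9.6 fixes the calendar, "All scheduled study visits are defined relative to Study Day 1, the date of first Induction Treatment Period dose", and then gives its own rule: "The last non-missing measurement taken prior to Day 1 (including unscheduled assessments) will be labeled as Baseline". Table 3, directly below, gives the baseline row for non-efficacy data, PGA and IBDQ as "Visit 1/Baseline n/a -14 [-28, -1] ≤1", so its analysis window includes Day 1. The endoscopy and biopsy row has the same window. After Table 3, the SAP says that when several results fall in one window, "the result with the date closest to the protocol Ideal Study Day will be used in the analysis". Ties go to the earliest measurement. Several assessments on one day are averaged, except laboratory data, where the earliest is taken.

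Two other places bear on the point. The footnote in SAP 12 says of PGA and the total Mayo score (MCS) that "these are Study Day 1 pre-dosing values". Protocol 6.5 says that Day 1 predose vital signs, from pulse and blood pressure to "temperature, and respiratory rate) will be used as baseline measurements".

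**The concern.** The 9.6 sentence and 9.5 cannot both be followed for anything measured on Day 1 before dosing. SAP 9.6 says that its convention covers all by-visit efficacy and safety analyses, and the SAP states no precedence between the two sections. The list of deviations from the protocol in SAP 18 does not mention baseline.

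Two kinds of harm could follow. Variables first collected on Day 1 would have no scheduled baseline, so endpoints that need one would be missing. Variables collected at both Screening and Day 1 would take the Screening value. That second error is the quieter one: a baseline exists for everyone, so no missing-data check would reveal it.

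**Working it through.** The plan gives no figure to reproduce here. The check sets each variable's schedule in Protocol Table 1 against each rule.

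**Inputs**
- Protocol Table 1: CRP, fecal calprotectin (FCP), PGA, Mayo Clinic score and IBDQ have no Screening entry and first appear at Visit 2 (Day 1). Vital signs, 12-lead ECG and haematology appear at both Screening and Visit 2. Endoscopy and biopsy before treatment are at Screening only.
- Footnote u of that table: stool is collected within 24 hours before the visit, so the Visit 2 sample may be dated Day −1 or Day 1.
- Footnotes j and l: on Day 1, ECG and vital signs are taken predose and at 1, 2, 4 and 6 hours postdose.
- SAP 9.3: there is no Day 0.

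**Which value becomes Baseline**

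| Variable | SAP 9.5 | 9.6 sentence | Table 3 window with closest-day rule |
|---|---|---|---|
| CRP, PGA, IBDQ | Day 1 predose | none scheduled | Day 1 |
| Partial Mayo score (PMS), total MCS (both need PGA) | Day 1 predose | none scheduled | Day 1 |
| FCP | Visit 2 sample | only if dated Day −1 | Visit 2 sample |
| Vital signs, ECG, haematology | Day 1 predose | Screening | Screening |
| Endoscopy, histology, and the stool frequency and bleeding scores tied to that endoscopy | Screening | Screening | Screening |

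**Why Table 3 still picks Screening in the fourth row.** The ideal day for the baseline visit is Day −14. A reading on Day −28 is 14 days away, one on Day −1 is 13 days away, and any reading between is no further than 14. Day 1 is 1 − (−14) = 15 away by day number, or 14 by calendar because there is no Day 0. Screening is therefore nearer, or at worst tied (Day −28, counted by calendar), and the tie goes to the earlier value. The exception is a Screening reading older than the usual window, which Protocol 8.1 allows when Screening is extended: Day −30 is 16 days away and loses to Day 1. The baseline chosen would then depend on how long Screening lasted.

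**Same-day averaging.** This matters only where Day 1 is the date selected. If only dates were compared, the five Day 1 vital-sign readings would be averaged, with one predose and four postdose readings contributing. The date-and-time clause in 9.5 prevents this where times are recorded. For ECG, SAP 17.5.1 takes the earlier assessment within a timepoint but does not say how Day 1 timepoints combine into a baseline. Laboratory data use the earliest value and do not have this problem.

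**What depends on the affected baselines**
- Clinical response by total MCS at Week 13, which needs a fall of at least 3 points and 30% from baseline (SAP 7.5, 16.3).
- Change from baseline in CRP, PMS, IBDQ and total MCS, and in FCP where the sample is dated Day 1 (SAP 16.4, Table 7).
- Subgroups by baseline CRP and total Mayo score, and by FCP with the same qualification (SAP 10.5).
- Stepwise models with baseline CRP; their baseline lymphocyte count would come from Screening (SAP 16.3).
- Multiple imputation under MAR for the primary and key secondary endpoints. SAP 16.1.4.1 allows no missing baseline in its variable list, which includes CRP and PGA, and excludes any participant who has one.
- Heart-rate and QTcF changes (SAP 17.5.1) and change in lymphocyte count, which would be measured from Screening.

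**What does not.** Clinical remission and the four key secondary endpoints are defined on Week 13 values alone (SAP 7.5), and their main analyses use strata from the randomization system. Response by modified Mayo score uses components already available at Screening.

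**The case against.** The best answer is that no competent programmer would be misled. SAP 9.5 is the baseline section, and its tie-break for untimed Day 1 values would have no purpose if Day 1 were excluded. The SAP 12 footnote agrees, and Table 11 in the imputation appendix starts PGA, FCP and CRP at Visit 2. Table 3 admits Day 1 in the row that names PGA and IBDQ, and its window is compatible with 9.5 because a Day 1 predose value has Study Day 1. Postdose readings are excluded by time under 9.5.

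Most of this stands, and it settles the intent. It does not remove the conflict. The 9.6 sentence is an operative rule with a different result, and Table 3 combined with the closest-day rule still leads to Screening for vital signs, ECG and haematology.

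Three stronger readings are tempting and are not supported:
- A reader might infer that the Day 1 variables have no baseline anywhere in 9.6, so that their endpoints cannot be computed. That follows from the sentence alone. Table 3 gives them a Day 1 baseline, and an unscheduled earlier value could supply one for some participants.
- A reader might infer that FCP always loses its baseline. The stool sample may be dated Day −1, which satisfies even the sentence.
- A reader might take Protocol 6.5 as setting the baseline for ECG and haematology. It does so for vital signs only. For the other two, the Day 1 predose value follows from SAP 9.5.

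**Conclusion.** The point holds as a conflict of text with consequences if 9.6 is programmed as written. The sentence disagrees with SAP 9.5, the SAP 12 footnote, Protocol 6.5 for vital signs, and Table 3 in its own section. Read literally, it leaves five measures (CRP, PGA, PMS, total MCS, IBDQ) without a scheduled baseline, makes FCP depend on the date of the stool sample, and replaces the Day 1 predose value of vital signs, ECG and haematology with a Screening value. Participants without baseline CRP or PGA would also drop out of the MAR imputation.

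It would be wrong to infer that the trial's main conclusions are at risk. The main analyses of the primary and key secondary endpoints are unaffected; of the analyses of those endpoints, the MAR sensitivity analysis and the subgroups named above are exposed. The rest is other-secondary, exploratory or descriptive safety output.

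The effect on the heart-rate threshold counts is not quantified, because the documents give no within-day or between-day variability for heart rate. The verdict assumes that assessments follow Protocol Table 1 and that Day 1 means the calendar date of first dose, as SAP 9.6 says.

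**What to change.** Make four small edits to SAP 9.6:
1. Replace the sentence on Baseline with a reference to the 9.5 rule.
2. Mark the Study Day ≤1 entry in the non-efficacy, PGA and IBDQ row of Table 3 as subject to 9.5: predose by date and time or, if time is missing, planned as predose.
3. Do the same for the ≤1 entry in the endoscopy and biopsy row.
4. In the text after Table 3, state that the closest-to-ideal-day and same-day averaging rules do not select Baseline.

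The cost is a few lines of text and a check that the analysis dataset specification follows 9.5. No new data are needed, and the sample size, the testing procedure and the main analyses do not change. The edits should be made before the interim database lock, so that no choice among baselines is left until after unblinding.

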16.3 Other Secondary Efficacy

Plasma concentrations of VTX002 will be handled in a separate PK Analysis Plan. Other secondary endpoints addressed in this SAP include the following (see [Section 7.2](#)):

- The proportion of participants with clinical response using MMS at Week 13
- The proportion of participants with endoscopic remission at Week 13
- The proportion of participants with endoscopic and histologic remission at Week 13
- The proportion of participants with endoscopic and clinical remission at Week 13
- The proportion of participants with endoscopic, histologic, and clinical remission at Week 13
- The proportion of participants with symptomatic remission at Weeks 4, 8, 10
- The proportion of participants with symptomatic response at Weeks 4, 8, 10, 13
- The proportion of participants with clinical remission using total MCS at Week 13
- The proportion of participants with clinical response using total MCS at Week 13
- The proportion of participants with histologic improvement at Week 13
- The proportion of participants with HEMI at Week 13
- The proportion of participants with any decrease from baseline in Geboes Index score at Week 13
- The proportion of participants with UC-related hospitalizations
- The proportion of participants requiring UC-related surgeries, including colectomy

These endpoints will be analyzed similarly to the primary endpoint, per timepoint, using the CMH test with the same as-randomized stratification factors. The FAS set will be used for this purpose and treatment group comparisons (VTX002 60 mg vs placebo; VTX002 30 mg vs placebo) will be as-randomized. No adjustment for multiplicity will be made.

Additionally, for clinical remission, endoscopic improvement, endoscopic remission, histologic improvement (Geboes), and histologic remission (Geboes) at Week 13, separate logistic regression models with stepwise selection will be built to assess the impact of the following covariates measured at baseline:

- ALC derived from blinded hematology laboratory results
- c-RP

Randomization stratification factors (from IWRS) will also be included in the stepwise selection. The alpha level for both entering and removing a covariate will be 0.10. Point estimates and the corresponding 95% CIs for the odds ratios will be calculated.

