22. APPENDIX I. MAYO SCORING SYSTEM

The Mayo score ranges from 0 to 12, with higher scores indicating more severe disease.

Stool frequency subscore: Each participant serves as his or her own control to establish the degree of abnormality of the stool frequency.

0=Normal number of stools for this participant

1=1 to 2 stools more than normal

2=3 to 4 stools more than normal

3=5 or more stools more than normal

Subscore: 0 to 3

Rectal bleeding subscore: The daily bleeding score represents the most severe bleeding of the day.

0=No blood seen

1=Streaks of blood with stool less than half the time

2=Obvious blood with stool most of the time

3=Blood alone passes

Subscore: 0 to 3

Findings on endoscopy (endoscopy subscore): The endoscopy subscore will be determined by qualified personnel at a central laboratory.

0=Normal or inactive disease

1=Mild disease (erythema, decreased vascular pattern)

2=Moderate disease (marked erythema, lack of vascular pattern, friability, erosions)

3=Severe disease (spontaneous bleeding, ulceration)

Subscore: 0 to 3

Physician's Global Assessment: The Physician's Global Assessment acknowledges the 3 other criteria, the participant's daily recollection of abdominal discomfort and general sense of well-being, and other observations, such as physical findings and the participant's performance status.

0=Normal

1=Mild disease

2=Moderate disease

3=Severe disease

Subscore: 0 to 3.

The following combinations of subscores are used in efficacy endpoints definitions:

Modified Mayo score (MMS): Endoscopy subscore + Rectal bleeding subscore + Stool frequency subscore;

Mayo Clinic score (MCS): Endoscopy subscore + Rectal bleeding subscore + Stool frequency subscore + Physician's Global Assessment;

Partial Mayo Score (PMS): Rectal bleeding subscore + Stool frequency subscore + Physician's Global Assessment.

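### Total Mayo score at Week 13 can be lost, and scored as non-response, when an out-of-window visit falls inside the endoscopy window but outside the narrower PGA window

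*SAP*

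**What the plan says.** SAP Section 9.6, Table 3, has two relevant rows. The row for non-efficacy data, which also covers "Global Assessment (PGA), IBDQ", has a Visit 7 window of Days 82-102 and a Visit 6 window of Days 64-81. The row for endoscopy and colonic biopsy has a Visit 7 window of Days 76-108.

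Footnote b ties other data to an in-window endoscopy: "the SF, RB, ES, and histopathology data are associated with Visit 1/Baseline or Visit 7 as appropriate". PGA is not named. Footnote d covers early-termination and unscheduled visits: "analysis visit windows are applied to ET and Unscheduled visit data in a manner identical to that of other visits".

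SAP Appendix I defines "Mayo Clinic score (MCS): Endoscopy subscore + Rectal bleeding subscore + Stool frequency subscore", with PGA as the fourth term. Section 9.6 adds that "if one or more components is missing from an analysis visit window the composite score is missing", and fixes the order of steps: "Windowing will be applied prior to any missing data calculations".

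SAP Section 16.3 lists "The proportion of participants with clinical remission using total MCS at Week 13" among the other secondary endpoints, together with clinical response by total MCS. It has them analyzed like the primary endpoint on the FAS, with no multiplicity adjustment. SAP Appendix VIII, Table 12, assigns non-responder imputation to other secondary endpoints when any one component is missing.

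**The concern.** Three of the four components of total MCS follow the endoscopy, and the fourth follows a narrower calendar window. A visit that records all four can therefore be split by the windowing step. The observed total MCS is discarded and a failure is put in its place, while MMS from the same visit stands. A participant could be a remitter by MMS and a failure by total MCS for a reason unrelated to disease.

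The text reads as an oversight. Section 9.6 names total MCS when it anchors RB and SF to the endoscopy or site visit, but leaves PGA under the general closest-day rule. Footnote a says the windows are meant to place all by-visit Induction data, yet a PGA on Days 103-108 has no home. A PGA on Days 76-81 goes to Visit 6, a telephone visit at which the protocol schedules no PGA and for which no PMS analysis is planned. The early-termination column of protocol Table 1 schedules endoscopy, PGA and the Mayo score together, so such a visit is designed to yield a complete score.

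**Working it through.** The plan gives no figure of its own on this point. The inputs are the Table 3 windows, the protocol visit window and the planned arm size.

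**1. Window widths (SAP Table 3).**
- Endoscopy: 108 - 76 + 1 = 33 days, which is Day 92 ± 16.
- PGA: 102 - 82 + 1 = 21 days, which is Day 92 ± 10.
- Days in the first but not the second: 33 - 21 = 12, namely Days 76-81 and 103-108.

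**2. Mapping of one visit that collects all four components.** This assumes enough eDiary days for SF and RB and no other PGA on Days 82-102.

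| Visit day | ES, SF, RB map to | PGA maps to | MMS | Total MCS |
|---|---|---|---|---|
| 76-81 | Visit 7 | Visit 6 | complete | missing, so non-response |
| 82-102 | Visit 7 | Visit 7 | complete | complete |
| 103-108 | Visit 7 | no visit | complete | missing, so non-response |

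**3. Protocol-timed visits.** The Visit 7 window is Days 89-95. Protocol Table 1, footnote a, allows Visit 7 assessments up to 7 days before the visit: 89 - 7 = 82, exactly the lower limit of the PGA window. The latest day, 95, is below 102. No visit within the protocol window is affected.

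**4. Split-day visits.** An endoscopy on Day 78 with the PGA at a visit on Day 85 (7 days later) maps wholly to Visit 7, and total MCS can be computed.

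**5. Size.** The documents do not say how many participants are assessed on the 12 days. With 63 per arm (SAP Section 6), each true total-MCS responder lost costs 1/63 = 1.6 percentage points of that arm's rate; two cost 2/63 = 3.2 and three cost 3/63 = 4.8.

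For an illustration on remission, assume that 2% to 5% of each arm is affected. Borrow the planned MMS remission rates of 28% on 60 mg and 8% on placebo (SAP Section 6) as an approximation.
- At 5%: 0.05 × 28 = 1.4 points on 60 mg and 0.05 × 8 = 0.4 on placebo, so 1.0 point off the difference.
- At 2%: 0.02 × 28 = 0.56 and 0.02 × 8 = 0.16, so 0.4 points off the difference.

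By the SAP Section 7.5 definitions, every total-MCS remitter is also an MMS remitter, so the planned total-MCS remission rates would be no higher than these. Total-MCS response would be more frequent, but the documents give no rate for it.

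**The case against.** The case for leaving this alone has real weight.

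- **Few participants are exposed.** Only early-termination, unscheduled or clearly mistimed visits can fall on the 12 days. This stands.
- **Exposure is not the same as a changed result.** A separate PGA on Days 82-102 rescues the score. Participants with an intercurrent event under SAP Section 16 are non-responders in any case, as are those whose observed score is not a response. This stands too, so it would be wrong to infer that everyone endoscoped on Days 76-81 or 103-108 becomes a total-MCS failure.
- **The share of days overstates the reach.** The 12 days are 36% of the endoscopy window (12/33), but that counts calendar days. It does not mean that a third of participants are affected, because visits are scheduled around Day 92.
- **The endpoints are low in the hierarchy.** Both are outside the multiplicity procedure, and protocol Section 3.2 describes endpoints beyond the primary and key secondary as descriptive. This stands and sets the severity.
- **The rule is the same in every arm.** With equal exposure it tends to shrink a true difference, as the illustration shows. Equal exposure is itself an assumption, since early termination may differ between arms.

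None of this removes the mechanism. No text in the SAP carries PGA with the endoscopy, so an observed score can still be replaced by a failure.

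**Conclusion.** The mismatch is real and minor. It operates when all four components come from a visit on Days 76-81 or 103-108 and no other PGA falls on Days 82-102. In that case total MCS is imputed as non-response at Week 13 although it was observed.

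Its reach is total-MCS clinical remission and clinical response. A reader might infer that the primary result is at risk; it is not, because neither the primary nor any key secondary endpoint uses PGA. A reader might also infer that Week 13 PMS and IBDQ gain false failures. They can lose observations on those days, but under SAP Section 16.4 PMS is modelled by MMRM without imputation and IBDQ is only summarized.

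The size is unknown from the documents. The firm figure is 1.6 points per true responder lost in an arm of 63. A loss near 5 points would need three affected participants in one arm, all of them true responders, and nothing in the documents supports that. The 0.4 to 1.0 point illustration for remission rests on the assumed 2% to 5% share and the borrowed MMS rates.

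**What to change.** In SAP Section 9.6, Table 3, footnote b, add PGA recorded at the same visit to the data that travel with the endoscopy, for computing total MCS at Visit 7. Where that visit has no PGA, the existing Table 3 rule can remain. With this change the days on which a complete same-visit score is lost fall from 12 of 33 to 0 of 33. It also avoids pairing the most recent endoscopy with a PGA from another visit that happens to lie closer to Day 92.

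Widening the whole PGA and IBDQ row to Days 76-108 is less clean. When no endoscopy maps to Visit 7, footnote c takes SF and RB from a site visit within the window, and Table 3 gives no separate window for them. If Days 82-102 apply there, a wider PGA window could create the reverse mismatch for PMS.

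The cost is one sentence in a footnote and the matching derivation; no new data are needed. It should be made before the interim lock and unblinding, so that it cannot look driven by results. A blinded listing of PGAs dated Days 76-81 or 103-108 would show whether anyone is affected.
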